MitoQ for Fatigue in Multiple
Sclerosis: A Placebo Controlled Trial

NCT04267926

September 23, 2021

Title

MitoQ for fatigue in multiple sclerosis: a placebo-controlled trial

Specific Aims/Purpose

Specific Aim 1: Determine whether Veteran's with MS (VwMS) who receive oral MitoQ in comparison to those who receive placebo have less fatigue after a 12-week treatment period as measured by MFIS Score.

Specific Aim 2: Determine whether VwMS who receive oral MitoQ in comparison to those who receive placebo have improved cognitive function, quality of life and depression using Symbol Digit Modality Test (SDMT), MS Impact Scale -29 (MSIS-29) and the Beck Depression Inventory–Fast Screen scores respectively.

Specific Aim 3: Determine the safety and tolerability of MitoQ in VwMS using side effects and blood tests.

Specific Aim 4: Determine whether plasma MitoQ levels in VwMS treated with MitoQ correlate with clinical outcomes of fatigue, cognitive function, quality of life and depression and with blood based inflammatory immune and oxidative stress biomarkers.

The proposed work is innovative; the

Hypothesis: The central hypothesis is that oral MitoQ with its mitochondrial affinity will improve MS related fatigue, cognition, quality of life and mood by improving mitochondrial function and resultant neuronal energy depletion in neurons.

Research Design and Methods

We propose to conduct a double-blind, placebo-controlled, pilot trial to compare the administration of a 20 and 40 mg dose of oral MitoQ to a placebo, as a treatment to reduce fatigue in MS subjects. There is no research to guide the study supplement dosage for this study. We have chosen 20 and 40 mg dosages based on correspondence from the manufacturer as noted above, in addition to the published recommendation in an article reviewing all the human and animal studies on MitoQ. The participation period for each subject will be 13 weeks: screening visit during the first week, followed by a 12-week treatment period. The study will require 4 visits and 4 phone calls over 13 weeks. Total time commitment is approximately 7 hours.

Overall Design

Aims	Outcomes	Description
1. Determine whether Veterans with MS who receive oral MitoQ in comparison to those who receive placebo have less fatigue after a 12-week treatment period as measured by MFIS Score.	Primary Outcome: MFIS Secondary Outcome: FSS	Double-Blind, randomized groups assigned to either 20 or 40 mg of MitoQ or an identical placebo. Check MFIS, and FSS and SDMT at time 0, 6 and 12 wks
2. Determine whether Veterans with MS who receive oral MitoQ in comparison to those who receive placebo, have improved cognitive function, quality of life and depression using SDMT, MSIS-29 and the BDI–FS scores respectively.	Secondary Outcome: SA-EDSS and BDI.	Double-Blind, randomized groups assigned to either 20 or 40 mg of MitoQ or an identical placebo. Check SA-EDSS and BDI at time 0 and 12 weeks
3. Determine the safety and tolerability of MitoQ in subjects with MS using side effects and blood tests.	Secondary Outcome: Safety.	Monitoring of patient response and reporting/recording AEs
4. Determine whether plasma MitoQ levels in Veterans with MS treated with MitoQ correlate with clinical outcomes of fatigue, cognitive function, quality of life, depression, blood inflammatory immune markers, and markers of oxidative stress.	Secondary Outcome: Plasma levels of oral MitoQ 1 hr post-drug. Plasma and/or PBMC IFN- γ , TNF- α , IL-2, IL-6 and IL-17, MDA, HAE, TAC, NOC and SOD	Data collection on MitoQ plasma levels and inflammatory and oxidative stress markers at baseline, week 6 and 12.

Subject Visits and Assessment Schedule

Table 2. Study Activities

	Week 0	Week 1	Week 7	Week 13	
	Visit 1	Visit 2	Visit 3	Visit 4	
Visit time	2 hours	2.5 hours	2.5 hours	2.5 hours	
Purpose	screen, consent	begin treatment	in clinic follow up	end treatment	Total blood draw amount
Consent	X				
Vital signs	X	X	X	X	
Medical history, physical neurological exam	X			X	
T25W, 9HPT, SDMT		X	X	X	
BDI, FSS, MFIS, MSIS-29	X	X	X	X	
Blood testing CBC w/ diff (4mls) CMP (6mls)	X		X	X	30 mls
Blood draw for plasma MitoQ level (4mls)		X	X	X	12 mls
Blood draw for Inflammatory immune markers 40 mls		X	X	X	120 mls
Medication reconciliation	X	X	X	X	
Urine testing (female)	X		X	X	
Side effect monitoring			X	X	

Specific Aim 1: Determine whether Veterans with MS who receive oral MitoQ in comparison to those who receive placebo have less fatigue after a 12-week treatment period as measured by MFIS Score. Our hypothesis is that MitoQ preserves or improves the mitochondrial function and that in turn may improve fatigue in MS therefore MS veterans taking MitoQ will have less fatigue than those Veterans with MS taking placebo.

Introduction: Fatigue, a common MS symptom can be a cause of significant disability, and loss in quality of life in Veterans with MS. While the mechanisms responsible for fatigue in MS are poorly understood it is possible that reversible mitochondrial dysfunction due to oxidative stress and resultant neuronal ATP depletion may contribute to fatigue. Orally administered MitoQ is a mitochondria-targeted antioxidant similar to CoQ10 but more effective in migration to mitochondria compared to CoQ10 and is aimed at reducing the effects of mitochondria-derived ROS, which lead to mitochondrial dysfunction. While a pilot study using CoQ10 for fatigue improvement in MS showed positive results, studies evaluating effects of oral MitoQ in MS have not been conducted.

Procedures: We will determine the effects of 20 or 40 mg oral MitoQ versus placebo on MS fatigue as measured by MFIS. We will obtain descriptive information about changes in MFIS scores for each subject group and will use the collected data to determine the mean, SD, and confidence interval of this change. This information will also help determine sample size and power analysis for a future phase II trial. This study will be the first to assess whether MitoQ changes fatigue in MS subjects. Data from MFIS scores taken at baseline assessment, and 6- and 12-week time points will be assessed, to determine changes in MFIS fatigue scores. The primary outcome measure will be the change from baseline total MFIS score to 12-week total MFIS score. Secondary outcome measures will be the change from baseline to each of the following measures: 6-week MFIS and 6 and 12-week FSS scores.

Statistical Analysis

Data Analysis: We will obtain descriptive information on primary and secondary outcomes. In particular, at each time-point, we will obtain the mean, median, SD, and range for each measure and for the changes from baseline for each measure, for the MitoQ and placebo subject groups. We will also obtain 95% confidence intervals for the changes from baseline for each measure, at each time point for both subject groups. We will conduct a t-test to compare primary and secondary measures (changes from baseline) and to obtain the associated 95% confidence intervals for the differences in mean change between the MitoQ and placebo subject groups. We will focus on the confidence intervals that describe the plausible differences in mean change between the subject groups. These confidence intervals will provide information about the magnitude of differences in MFIS and FSS changes between subject groups that are consistent with the previous data. We will also test for differences in the change scores by group in a linear regression framework, adjusting for demographic and clinical characteristics, such as gender. As a secondary analysis, we will use an ANCOVA test with 12-week MFIS score as the outcome and baseline MFIS score as a covariate to account for baseline differences in fatigue among patients. We will use a linear mixed model to analyze MFIS changes over time with fixed effects for time, incorporating baseline values of the outcome as a covariate, and random intercepts and slopes for individuals to incorporate within-subject variability. Due to the exploratory nature of this study, the 6 week time point will provide evidence of whether or not change is seen by 6 weeks. It will allow us to understand how long MitoQ takes to have an effect, and this information will be useful for planning future studies. Both formal hypothesis testing and confidence interval estimation will be conducted. To detect a trend in the effect of MitoQ dosage, we will perform an ANOVA trend analysis on the change in MFIS between baseline and 12 weeks among the three treatment groups. In addition, we will categorize participants who improved by a reliable change, defined as differences in group means divided by the standard error, greater than 1.96 points and test for differences in the proportion of improvers by group using a chi-squared test. The standard error is given by $s_1\sqrt{1 - r_{xx}}$, where s_1 is the standard deviation of the control group and r_{xx} is the MFIS test-retest reliability (here, given by the MFIS Cronbach's alpha value of 0.81.⁶ This analysis will yield additional power (compared to a 2-sample t-test) and will provide useful data for planning a repeated measures analysis in a future larger trial. Secondary outcomes will be analyzed in the same manner. To test if the effect of MitoQ on FSS depended on compliance, compliance (as measured by pill counting) will be treated as a co-variate in the analyses. Patterns of missing data will be examined to determine if patient characteristics are related to missing follow-up data. Statistical significance is defined as $P < 0.05$. SPSS for Windows Version 15.0 (SPSS Inc., Chicago) and SAS (SAS Institute, Cary, NC) will be used for analysis.

Anticipated results: We expect that MS veterans taking MitoQ for 12 weeks will have less fatigue than those Veterans with MS taking placebo as determined by the MFIS.

Specific Aim 2: Determine whether Veterans with MS who receive oral MitoQ in comparison to those who receive placebo have improved cognitive function, quality of life and depression using Symbol Digit Modality Test (SDMT), MS Impact Scale -29 (MSIS-29) and the Beck Depression Inventory–Fast Screen scores respectively. Our hypothesis is that by improving mitochondrial function in sub optimally functioning neurons and axons, MitoQ, an efficient mitochondrial targeted therapy, may lead to cognition, quality of life and depression improvement in Veterans with MS.

Introduction: In addition to fatigue, cognitive impairment, poor quality of life and depression are some aspects of MS that have significant adverse impact on patient's lives and not addressed by current treatment options including the disease modifying therapies. Mitochondrial targeted therapy CoQ10 has shown significant improvement in depression (BDI) and quality of life in a small pilot study as compared to placebo.⁴⁶ Since MitoQ is considered to have better mitochondrial penetration than CoQ10, it is worthy of exploring its effects on these poorly managed MS symptoms.

Procedures: At baseline assessment and visits 3 and 4 (6 and 12-week post treatment initiation assessment). At each of these visits, we will also acquire data on each subject's cognitive function using SDMT, quality of life assessment using MSIS-29 and depression using BDI-FS scores.

Statistical Analysis: Exploratory analyses similar to the primary analysis including mixed model that will account for repeated measures will be conducted using the SDMT, MSIS-29 and BDI-FS as the secondary outcome measures. To test if the effect of MitoQ depended on changes in depression a similar model will be constructed including both the baseline and the end of the period BDI-FS. The effect of MitoQ on depression will be evaluated by fitting a model with BDI-FS at the end of each period as the outcome. Baseline values for the SDMT, MSIS-

29, BDI-FS and FSS will be included as covariates, and patient effects treated as random. Changes in activity over time will be analyzed in an exploratory manner using graphical techniques.

Anticipated results: We expect that MS veterans taking MitoQ will have better cognition and quality of life and less depression than those Veterans with MS taking placebo as determined by the standard measures.

Specific Aim 3: Determine the safety and tolerability of MitoQ in subjects with MS using side effects and blood tests.

Introduction: Results from clinical trials in Hepatitis C and PD as described in the “current status of the field section” suggested that MitoQ is generally well-tolerated and no safety concerns surfaced. To assess the safety and tolerability of oral MitoQ versus a placebo, all subjects (treatment as well as the placebo groups) will undergo monitoring for AEs and side-effects as described below. An adverse event is any untoward medical occurrence (signs, symptoms, intercurrent illness or abnormal lab findings) that occurs in a study subject during the treatment or cross over periods, regardless of suspected cause.

Statistical Analysis: To evaluate patient safety, laboratory test results at baseline and changes from baseline at 6 and 12 weeks will be determined and summarized for each subject group, and will be compared using t-tests for continuous measures and Fisher’s exact test for proportions.

Anticipated results: We expect that MS veterans taking MitoQ will have no significant and unexpected AE on their blood tests and body systems than those Veterans with MS taking placebo.

Specific Aim 4: Determine whether plasma MitoQ levels in Veterans with MS treated with MitoQ correlate with clinical outcomes of fatigue, cognitive function, quality of life, depression, blood inflammatory immune markers, and markers of oxidative stress. We will test the hypothesis that plasma concentrations of MitoQ correlate with fatigue, cognitive function, quality of life and depression in subjects with MS receiving MitoQ compared with those receiving placebo. Additionally, this aim will test the hypothesis that MitoQ will lower the blood concentration of inflammatory immune markers and markers of oxidative stress. We hypothesize that MS subjects receiving MitoQ will have improved levels of blood biomarkers of oxidative stress as seen by lower lipid peroxidation (LPO) products, nitric oxide catabolites (NOC) and superoxide dismutase (SOD) activity and improved TAC.

Introduction: Pharmacokinetic (PK) studies of oral MitoQ have been conducted in healthy human subjects but not in MS. Healthy human PK studies suggest maximal plasma concentration (Cmax) of MitoQ after oral dosing at 40 mg (0.5 mg/kg) and 20 mg (0.25 mg/kg) to have detectable and maximal concentration ~1hr. Limited CoQ10 studies in MS suggest significant impact on cytokine and oxidative stress biomarker profile hence we believe that MitoQ may have similar effects too. We now have good in vitro data on the ability of MitoQ to suppress LPS-induced cytokine production in human peripheral blood mononuclear cells and this study will provide a novel opportunity to explore the biologic effects of MitoQ. With the data collected on clinical outcomes such as fatigue, cognition, depression and QOL in this study, we will be able to generate pilot data correlating the PK, immune markers and these clinical outcomes.

Statistical analysis. We will construct Q-Q plots on all data to test for normalcy. Using Pearson correlations for parametric data or Spearman Rho correlations for nonparametric data, we will determine linear associations among changes in cytokines including IFN- γ , TNF- α , and IL-2 and plasma levels of MitoQ. We will use repeated measures mixed effects models to investigate the linear relationships between pro-inflammatory markers, oxidative stress biomarkers, cytokines, and MitoQ levels over time (i.e., at 6 and 12 weeks). We will examine correlation between measures of oxidative stress as well as the correlation between oxidative stress markers and plasma levels of MitoQ. We will obtain mean changes from baseline to 12 weeks and 95% confidence intervals for the oxidative stress markers. The correlations, means, and standard deviations observed in the oxidative stress biomarkers of this study will help inform power and sample size calculations in future trials. Statistical significance is defined as $P < 0.05$.

Anticipated results: We expect that plasma concentrations of MitoQ will correlate with fatigue, cognitive function, quality of life and depression in subjects with MS and that subjects receiving MitoQ will have lower blood concentration of inflammatory and oxidative stress markers.

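### Side-effect enquiry is scheduled only 6 and 12 weeks after the first dose, with no matching pre-dose check and no stated timing or content for the four phone calls

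*Combined protocol and SAP*

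**What the plan says.** The row "Side effect monitoring" in Table 2 (Study Activities) has marks at Visit 3 (week 7) and Visit 4 (week 13) and is blank at Visits 1 and 2. The purpose given for Visit 2 (week 1) is "begin treatment".

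Research Design and Methods describes a "screening visit during the first week, followed by a 12-week treatment period" and adds: "The study will require 4 visits and 4 phone calls over 13 weeks". The calls have no column or row in Table 2, and no section gives their dates or purpose.

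For Aim 3, the Overall Design table gives the safety method as "Monitoring of patient response and reporting/recording AEs". The Introduction to Specific Aim 3 says that all subjects "will undergo monitoring for AEs and side-effects as described below". What follows is an AE definition, covering any untoward occurrence "that occurs in a study subject during the treatment or cross over periods, regardless of suspected cause", and then an analysis of laboratory results. No instrument, question set or collection schedule is described, and there is no rule for symptoms already present before treatment.

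**The concern.** Side effects are one of the two measures named for Specific Aim 3; blood tests are the other. The plan itself says that oral MitoQ has not been studied in MS and that no research guides the dosage here, so tolerability at the two doses is a main product of this pilot.

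On the schedule as written, a participant who has a short or mild problem in the first weeks is first asked about it, at a scheduled contact, up to 6 weeks later. Such events are easily forgotten or misdated. Pill counts can show that capsules were missed, but not why.

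There is also no pre-dose answer to the same question. Many people with MS have symptoms that could be reported as side effects. The blood tests have a baseline and a change from baseline; the side-effect enquiry has neither.

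**Working it through.** **1. Timing.** Inputs are the Table 2 week labels: treatment starts in week 1, and side-effect enquiries fall in weeks 7 and 13.

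- First dose to first enquiry: 7 − 1 = 6 weeks.
- First to second enquiry: 13 − 7 = 6 weeks.
- First dose to second enquiry: 13 − 1 = 12 weeks.

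This reproduces the plan's own figure. Specific Aim 2, Procedures, places "visits 3 and 4 (6 and 12-week post treatment initiation assessment". Scheduled enquiries before dosing: 0. During treatment: 2. Phone calls with any stated task: 0 of 4.

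**2. Are the blanks in the table genuine?** The marks in the blood rows agree with the stated totals: 3 × (4 + 6) = 30 mL, 3 × 4 = 12 mL and 3 × 40 = 120 mL. The column layout therefore appears intact, and the blanks at Visits 1 and 2 look real.

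**3. What the calls could do.** With k evenly spaced calls that ask about side effects in a 6-week interval, the gap between enquiries is 6/(k + 1) weeks.

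| Calls per interval | Gap in that interval |
|---|---|
| 0 | 6 weeks |
| 1 | 6/2 = 3 weeks |
| 2 | 6/3 = 2 weeks |

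The call dates are not given, so the even spacing is an assumption. If all four calls fell in one interval, or before the first dose, the longest gap would still be 6 weeks.

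**4. What is recorded before dosing.** Visit 1 has the medical history, physical neurological examination and blood tests. BDI, FSS, MFIS and MSIS-29 are taken at Visits 1 and 2, and T25W, 9HPT and SDMT at Visit 2. Vital signs and medication reconciliation are done at both. These capture many MS symptoms, but none is marked as a side-effect enquiry to set against Visits 3 and 4.

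**5. Direction of the effect on the comparison.** Let p be the true proportion of participants with a side effect, c the proportion of those that is recorded, and b the proportion with an independent pre-existing symptom that is counted. All values below are assumed for illustration; none comes from the plan.

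Recorded proportion = 1 − (1 − c·p)(1 − b), so the recorded difference = c(1 − b) × the true difference.

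| Assumption | MitoQ | Placebo | Difference |
|---|---|---|---|
| True rates | 30% | 10% | 20 points |
| Half forgotten (c = 0.5, b = 0) | 15% | 5% | 10 points |
| Pre-existing counted (c = 1, b = 0.4) | 58% | 46% | 12 points |
| Both (c = 0.5, b = 0.4) | 49% | 43% | 6 points |

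Errors of equal size in blinded arms still shrink the contrast. The second error does so while raising the rate in both arms.

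**The case against.** The strongest reply is that silence is not evidence of absence. Table 2 has columns only for the four visits, so the calls' absence from it says nothing about what they ask. The document also refers to material it does not contain, such as a section on the current status of the field, and a call script or AE procedure may sit there. A reader might infer that the calls carry no safety task. The document does not support that: it gives them no task of any kind.

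Second, AE capture is not confined to the two marks in Table 2. The plan commits to monitoring and recording AEs throughout treatment, so spontaneous reports are not excluded. It would go too far to say that all early intolerance rests on recall; that holds for scheduled enquiry only.

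Third, a reader might infer that pre-existing MS symptoms will be counted as side effects. No section says so, and a definition tied to what occurs during treatment can be read as leaving out unchanged earlier symptoms. The pre-dose record is also substantial.

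Fourth, the trial is randomised and double-blind, so neither error is shown to favour an arm, and counting old symptoms would make absolute tolerability look worse.

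These replies narrow the point. They leave standing the two marks in Table 2, the blank at Visit 2, the missing rule for pre-existing symptoms, and the shrinkage of the between-arm difference.

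**Conclusion.** The point holds in limited form. By Table 2, scheduled side-effect enquiry takes place twice, 6 and 12 weeks after the first dose, and never before it. The timing and content of the four calls are not stated in this document. Followed as written, the scheduled side-effect data for Aim 3 rest on two 6-week recalls, supplemented by whatever participants report unprompted, without a matching pre-dose check.

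The likely consequence is a diluted comparison with placebo. The plan's anticipated result for Aim 3 is framed as no important excess over placebo, so dilution leans towards the expected answer. The stronger claim, that both errors make MitoQ look well tolerated, is not supported: under-recording lowers AE rates, but counting pre-existing symptoms raises them. The two agree only in their effect on the contrast.

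The size of the dilution cannot be estimated from the document, because it gives no AE rates or recall figures. If the calls already ask about side effects, much of the recall problem disappears and the remedy there is only to write it down; the missing pre-dose check would remain. This is a worthwhile, inexpensive improvement to a pilot, not a fault that undermines the trial.

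**What to change.** - Mark side-effect monitoring at Visit 2, before the first dose, using the same checklist as at Visits 3 and 4.
- Add the four planned calls to Table 2 with their timing and a side-effect enquiry, placing some between Visits 2 and 3.
- Record the onset date of each symptom.
- In the AE comparison, count symptoms that are new or worse than at the pre-dose check.
- Put the collection procedure in the Specific Aim 3 text, where monitoring is promised but not described.

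The changes are to Table 2, the Aim 3 text and the case report form. Visit 2 and the calls are already planned, so no contact need be added, provided that some calls fall, or can be moved, between Visits 2 and 3. The cost is a few more minutes per contact and probably more recorded AEs in every arm, which should be expected when absolute rates are read.

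### MFIS is scheduled at two visits up to treatment start but only one score serves as baseline; averaging both would make the primary comparison more precise, by an amount the documents cannot fix

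*Combined protocol and SAP*

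**What the plan says.** Specific Aim 1, Procedures, sets the primary endpoint: "The primary outcome measure will be the change from baseline total MFIS score to 12-week total MFIS score". Under Statistical Analysis, Data Analysis, the t-test, the dose-trend ANOVA and the mixed model all rest on a baseline MFIS, and a secondary analysis uses it again: "we will use an ANCOVA test with 12-week MFIS score as the outcome and baseline MFIS score as a covariate". Secondary outcomes are to be handled in the same way.

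Table 2 (Study Activities) has one row for "BDI, FSS, MFIS, MSIS-29". It is marked at all four visits: Visit 1 (Week 0, screening and consent), Visit 2 (Week 1, treatment begins), Visit 3 (Week 7) and Visit 4 (Week 13). The row for SDMT and the two motor tests starts only at Visit 2.

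The Overall Design table, Aim 1 row, lists a single pre-treatment time point: "Check MFIS, and FSS and SDMT at time 0, 6 and 12 wks". No sentence names the visit that supplies baseline MFIS or says what becomes of the other score.

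**The concern.** A single questionnaire score carries visit-to-visit noise, and a change score takes all of that noise into the primary comparison. It also weakens baseline MFIS as a covariate. The trial will hold two scores about a week apart, and using only one gives up precision that has already been paid for. The plan states no sample size, power or MFIS standard deviation. It describes itself as a pilot, with emphasis on the confidence intervals for the group difference, so any gain would appear directly as narrower intervals.

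A smaller point is that the baseline visit, and whether its questionnaires come before the first dose, have to be inferred.

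**Working it through.** **Step 1: which visit is baseline?** The passages agree on Visit 2.
- Research Design and Methods describes a "screening visit during the first week, followed by a 12-week treatment period", so Visit 1 lies before treatment.
- Visits 2, 3 and 4 are at Weeks 1, 7 and 13. Measured from Visit 2 that is 0, 6 and 12 weeks. Measured from Visit 1 it is 1, 7 and 13, and no visit falls at 6 or 12.
- The Aim 1 row puts MFIS and SDMT at the same time 0, and SDMT is not done at Visit 1.
- Specific Aim 2, Procedures, reads: "At baseline assessment and visits 3 and 4 (6 and 12-week post treatment initiation assessment". Weeks are thus counted from treatment start.
- The Aim 4 row schedules plasma levels and markers at baseline and weeks 6 and 12. Table 2 has these draws only at Visits 2, 3 and 4.

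**Step 2: is the Visit 2 score taken before the first dose?** The documents do not say. A plasma draw is scheduled at Visit 2, and the Aim 4 outcome is "Plasma levels of oral MitoQ 1 hr post-drug", so dosing during that visit is possible.

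**Step 3: gain for the change score.** The plan gives no figure to reproduce. Assume equal variance s² at each visit. Let r12 be the correlation between Visits 1 and 2, and r1 and r2 their correlations with week 12.
- Visit 2 baseline: variance = 2s²(1 − r2).
- Mean of both: variance = s²[1 + (1 + r12)/2 − (r1 + r2)].
- Difference: s²[(1 − r12)/2 − (r2 − r1)].
- If r1 = r2 = r, the proportional cut is (1 − r12)/[4(1 − r)].

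If r12 = r as well, the cut is 1/4 for every r. At r = 0.81 the variance goes from 0.380s² to 0.285s², and the SD falls by 13.4%.

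The only correlation-type figure in the plan is the MFIS reliability of 0.81 (Data Analysis). It is labelled test-retest but is a Cronbach's alpha, so using it for r12 is an assumption. All values of r are assumed, as is r12 = 0.90.

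| r12 | r with week 12 | Cut in change-score variance |
|---|---|---|
| 0.81 | 0.75 | 0.19/1.00 = 19% |
| 0.81 | 0.70 | 0.19/1.20 = 16% |
| 0.81 | 0.60 | 0.19/1.60 = 12% |
| 0.81 | 0.50 | 0.19/2.00 = 9.5% |
| 0.90 | 0.80 | 0.10/0.80 = 12.5% |
| 0.90 | 0.70 | 0.10/1.20 = 8% |
| 0.90 | 0.60 | 0.10/1.60 = 6% |
| 0.90 | 0.50 | 0.10/2.00 = 5% |

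Simulation with 400,000 draws agreed. At r12 = 0.81 and r = 0.81, 0.60 and 0.50 it gave cuts of 24.8%, 12.0% and 9.4%.

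**Step 4: gain for ANCOVA.** With r1 = r2 = r, the residual variance (in units of s²) is 1 − r² with one baseline and 1 − 2r²/(1 + r12) with the mean. At r12 = 0.81:
- r = 0.50: 0.750 to 0.724, a cut of 3.5%.
- r = 0.60: 0.640 to 0.602, a cut of 5.9%.
- r = 0.70: 0.510 to 0.459, a cut of 10%.
- r = 0.81 (all equal): 0.344 to 0.275, a cut of 20%.

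**Step 5: if Visit 1 predicts week 12 less well.** Take r2 − r1 = 0.05 and r12 = 0.81. The change-score cut is (0.095 − 0.05)/[2(1 − r2)]: 4.5%, 5.6% and 7.5% at r2 = 0.50, 0.60 and 0.70. The ANCOVA cut is then −0.1%, 0.8% and 2.6%.

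**Step 6: what this is worth.** For an assumed standardised effect of 0.5, two-sided 0.05 and 80% power, 63 per arm are needed. A 25% variance cut reduces this to 48, a 12% cut to 56 and a 6% cut to 60.

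**The case against.** The strongest reply is that one baseline at treatment start is valid, unbiased under randomisation and conventional, so averaging is only a preference. It is right that nothing here makes the planned test invalid. Nor is a gain certain. For the change score, averaging loses precision if r2 − r1 exceeds (1 − r12)/2, which is 0.095 at r12 = 0.81 and 0.05 at r12 = 0.90. A gap of 0.095 would be large for visits a week apart. A smaller gap already removes most of the ANCOVA gain (step 5).

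Three downsides also stand.
- The supplied text has no eligibility section. If screening MFIS gates entry, Visit 1 scores would be raised by selection, and within-arm changes from an averaged baseline would contain regression to the mean. The equal-variance figures above would then be only approximate. The randomised comparison would not be biased, because the shift is the same in every arm on average.
- The plan wants the SD of change for sizing a later trial. An averaged-baseline SD would be too small for a trial with one baseline.
- The reliable-change standard error is a single-score formula.

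Three stronger readings are tempting, and the documents do not support them.
- A reader might infer that time 0 means Week 0, or that the analyst may choose between two primary results. The five passages in step 1 all point to Visit 2, so what is missing is an explicit statement.
- A reader might infer that averaging cuts the variance by a quarter whatever the correlation. That requires scores 1 week apart to correlate no more strongly than scores 12 to 13 weeks apart, which nothing in the documents supports.
- A reader might take both scores as certainly pre-treatment. The order at Visit 2 is not stated.

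**Conclusion.** The point holds as a low-cost gain in precision, together with a missing statement about which score is baseline and when it is taken. It is not an error that threatens the validity of the primary comparison. Under equal variances the 25% cut in change-score variance is close to a best case, and 5% to 19% is more realistic if correlation decays with time. If Visit 1 also correlates 0.05 less with week 12 than Visit 2 does, the cut is 4.5% to 7.5%. The ANCOVA gain is smaller under decay and could be close to nil in that last case. Every figure depends on assumed correlations, including the use of 0.81 as the one-week correlation.

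**What to change.** Before unblinding, add to the analysis plan:

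1. The Visit 2 questionnaires are completed before the first dose.
2. Baseline for MFIS, FSS, BDI-FS and MSIS-29 is the mean of the Visit 1 and Visit 2 scores, or the single available score if one is missing. Baseline for SDMT is Visit 2.
3. This baseline is used for the between-group change score and as the covariate in the ANCOVA and mixed models.
4. Within-arm changes, and the SD of change intended for future sample-size planning, are also reported from Visit 2 alone. The reliable-change analysis keeps the single-score Visit 2 baseline.

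If the sponsor prefers Visit 2 alone throughout, that is defensible, but it should be written down with the pre-dose condition.

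The cost is a few sentences in the plan and a second set of descriptive summaries. No visit or assessment is added, because Table 2 already schedules both scores.
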